### **10.3 Reporting Procedure for AEs, SAEs, and Pregnancy**

#### **10.3.1 Adverse Events**

All AEs either observed by the Investigator or one of his/her medical collaborators, or reported by the subject spontaneously, or in response to a direct question, will be noted in the AE section of the subject's eCRF and source documentation. This applies to all AEs regardless of presumed relationship to the study treatment. Adverse events leading to discontinuation of study treatment must be collected.

If any AE is reported, the date of onset, relationship to study treatment, any action taken, date of resolution (or the fact that it is still continuing or has become chronic), outcome, and whether the AE is serious or not, will be recorded. Use of colloquialisms and abbreviations should be avoided. Only 1 AE term should be recorded in the event field on the AE eCRF. Where possible, the Investigator should report a diagnosis rather than signs and symptoms or

abnormal laboratory values. However, if a constellation of signs and/or symptoms cannot be medically characterized as a single diagnosis or syndrome at the time of reporting, each individual event should be recorded on the AE eCRF. If a diagnosis is subsequently established, all previously reported AEs based on signs and symptoms should be nullified and replaced by one AE report based on the single diagnosis, with a starting date that corresponds to the starting date of the first symptom of the eventual diagnosis.

The AE reporting period begins at the time the ICF is signed by the subject. The AE reporting period ends at Visit 15 (if the subject participates in the continuation study) or the study follow-up visit (Visit 16), if the subject does not participate in the continuation study. Adverse events persisting at the time of study completion will be followed by the Investigator through contact with the subject until resolution or stabilization has occurred (or the subject is lost to follow-up and cannot be contacted) and recorded in the source documents. If the subject reports an AE, it is the Investigator's responsibility to acquire sufficient information in order to assess causality. This may require additional laboratory testing, physical examinations, telephone contacts, etc. In circumstances where the Investigator is unable to make contact with the subject, the Investigator must provide a written statement to Aurinia confirming that the subject is lost to follow-up.

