### 3 ENDPOINTS

#### 3.1 Primary Endpoint

Renal response at Week 52 will be adjudicated by the Clinical Endpoints Committee (CEC) based on the following parameters:

- UPCR of  $\leq 0.5$  mg/mg, and
- eGFR  $\geq 60$  mL/min/1.73 m^2 or no confirmed decrease from baseline in eGFR of  $>20\%$ , and
- Received no rescue medication for LN (see Protocol Section 7.8, Prohibited Therapy and Concomitant Treatment), and
- Did not receive more than 10 mg prednisone for  $\geq 3$  consecutive days or for  $\geq 7$  days in total during Weeks 44 through 52, just prior to the renal response assessment

The CEC will also take into account the following:

- Subjects who withdraw from the study prior to the Week 52 assessment and provide insufficient week 52 data to determine response will be defined as non-responders. Subjects who discontinue study drug but continue to attend study visits (as is the expectation) will have their data assessed for response.
- eGFR values eliminating a subject from complete remission should be accompanied by a treatment or disease-related treatment-emergent adverse event (TEAE) that impacts eGFR. Full details are given in Section [6.11.1](#).
- The CEC is independent and blinded from the treatment groups.

The primary endpoint estimand is the proportion of subjects showing renal response as adjudicated by the CEC in the ITT population when comparing voclosporin and placebo at Week 52. It is assessed in all randomized subjects who were recruited according to the inclusion/exclusion criteria of the protocol.

The variable is binary and indicates a response if a subject shows, at 1 year, adequate UPCR with no signs of detrimental impact on eGFR. Subjects who cannot be shown to be responders through their 1 year data (or absence thereof) are defined as non-responders.

Intercurrent events include:

- Treatment discontinuation for any reason
  - the subject remains on study, allowing the primary endpoint to be assessed at 1 year.
- Study discontinuation
  - resulting in insufficient information at 1 year to ascertain response status leading to assumed non-response.
- Rescue medication taken at any time prior to the primary assessment at 1 year
  - results in non-response. Rescue medication is adjudicated by the Clinical Endpoints Committee.
- Death at any time prior to the 1 year primary assessment
  - results in assumed non-response.

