## 4 SAMPLE SIZE

The total sample size will be approximately 324 subjects (162 subjects per treatment arm). This is based on the following assumptions:

- A two group continuity corrected Chi square test with a 0.05 two-sided significance level will have 80% power to detect the difference between a placebo response rate of 20.0% and a voclosporin response rate of 34.4% (odds ratio=2.1) when the sample size in each group is 162 (total N=324).
- The effect of withdrawals will be investigated. Subjects withdrawing for any reason will be counted as non-responders in the primary analysis and therefore no adjustment of sample size for withdrawals is necessary.
- The impact of withdrawals on primary endpoint will be investigated in the tipping point analysis.

Table 4.1 shows the voclosporin response rates required to maintain a minimum 80% power at the planned sample size for given placebo response rates. These response rates all lead to odds ratios of around 2, which is a clinically relevant effect.

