### 6.11.1 Primary Endpoint

The primary endpoint is the number of subjects showing renal response at 52 weeks. Renal response at Week 52 will be adjudicated by the CEC based on the following parameters:

- UPCR of  $\leq 0.5$  mg/mg, and
- eGFR  $\geq 60$  mL/min/1.73 m^2 or no confirmed decrease from baseline in eGFR of  $>20\%$ , and
- Received no rescue medication for LN, and
- Did not receive more than 10 mg prednisone for  $\geq 3$  consecutive days or for  $\geq 7$  days in total during Weeks 44 through 52, just prior to the renal response assessment

The CEC will be blind to treatment group and completely independent of Aurinia. They will also take into consideration the following:

- Subjects who withdraw from the study prior to the Week 52 assessment and thus provide insufficient Week 52 data will be defined as non-responders
- Medication listings will be reviewed by the CEC as part of the adjudication process. The CEC will have complete autonomy to adjudicate any treatment as rescue medication. However, as any dose of MMF is permitted within this protocol there is no MMF dose level that necessarily classifies it as being rescue medication. As part of this review the CEC will also adjudicate on steroid drug use beyond the protocolled taper.

- eGFR values eliminating a subject from complete remission should be accompanied by a treatment or disease-related TEAE that impacts eGFR. To this end, eGFR measures which would ordinarily result in a subject not being in remission will only be used if the first eGFR assessment occurs on a date where there is also a treatment or disease-related, eGFR associated TEAE. The following is a list of MedDRA preferred terms that are associated with eGFR decreases:
  - BLOOD CREATININE INCREASED
  - CREATININE RENAL CLEARANCE DECREASED
  - GLOMERULAR FILTRATION RATE DECREASED
  - SERUM CREATININE INCREASED
  - RENAL IMPAIRMENT
  - RENAL FAILURE
  - RENAL FAILURE ACUTE
- Confirmation of eGFR decreases from baseline require that two consecutive measures at least 3 days apart exhibit the decrease.

The null hypothesis  $H_0$  will be rejected in favor of  $H_1$  if there is evidence at the 5% significance level using a 2-sided test.

$H_0$ : There is no statistically significant difference in renal response between voclosporin and placebo at Week 52

$H_1$ : There is a statistically significant difference in renal response between voclosporin and placebo at Week 52.

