- Did not receive more than 10 mg prednisone equivalent for  $\geq 3$  consecutive days or for  $\geq 7$  days in total during Weeks 44 through 52, just prior to the renal response assessment
- “eGFR success” will also be summarized by individual components:
  - eGFR  $\geq 60$
  - eGFR  $< 60$  with no confirmed decrease  $> 20\%$
  - eGFR  $< 60$  with confirmed decrease  $> 20\%$  but with no disease-related or treatment-related eGFR associated AE present at time of assessment.

Confirmed decrease  $> 20\%$  in eGFR is two consecutive measurements, three or more days apart by the visit where response is defined.

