### 6.13.1 Adverse Events

A treatment emergent adverse event (TEAE) is defined as:

- Any AE that has an onset on or after the first dose of study drug up to last dose + 30 days. For subjects consenting to the AURORA 2 continuation study there will be an additional constraint to the TEAE definition: events must have an onset date prior to the first dose of AURORA 2 study drug.

A treatment-related TEAE is defined as a TEAE that is assessed by the Investigator or Sponsor as being related to study drug. If a TEAE has a missing relationship to study drug it is assumed to be related to the study drug for analysis purposes.

A disease-related TEAE is defined as a TEAE that is assessed by the Investigator or Sponsor as being related to the disease under study. If a TEAE has a missing relationship to the disease under study it is assumed to be related to the disease under study for analysis purposes.

Missing severity assessments will be summarised as severe.

The following tables will be presented for AEs:

- Summary table of overall incidence, the number of events, risk difference and 95% CI (voclosporin-placebo) including the following top line summaries:
  - Any AE
  - Any TEAE
  - Any Treatment-Related TEAE
  - Any Serious TEAE
  - Any Treatment-Related Serious TEAE
  - Any TEAE Leading to Voclosporin/Placebo Discontinuation
  - Any TEAE Leading to Death
  - Treatment-Related TEAE Leading to Death
  - Disease-Related TEAE
  - Disease-Related Serious TEAE

Detailed list of AE tables is given at the end of this SAP.

In counting the number of AEs reported, a continuous event (i.e., reported more than once and which did not cease), will be counted only once for a subject; a non-continuous AE reported several times by the same subject will be counted as multiple events.

Additional tables for serious TEAEs will be provided for each of the four regions: North America, Latin America, Europe/South Africa and Asia Pacific. Similar tables will also be provided for serious TEAEs occurring between day 1 and day 84 (Up to week 12), day 85 to day 168 (Week 12 to 24) and greater than day 168 (after week 24).

All AEs will be listed and a glossary of unique verbatim terms with coding information will be provided.

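### The eGFR criterion of renal response ignores a related renal adverse event that starts more than 30 days after last dose, and SAP 6.11.1 and 6.11.2.3 disagree on such a subject

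*SAP*

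**What the plan says.** SAP 6.11.1, and more briefly SAP 3.1, attach an adverse-event condition to the eGFR part of the primary endpoint. A value that would rule out response is used only if its first assessment falls on a date with a TEAE that is related to treatment or disease and associated with eGFR. "The following is a list of MedDRA preferred terms that are associated with eGFR decreases" then introduces seven terms. Four are laboratory findings (two for raised creatinine, one each for reduced creatinine clearance and reduced GFR). Three are conditions (renal impairment, renal failure, acute renal failure). Nothing admits other terms.

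SAP 6.13.1 defines a TEAE as "Any AE that has an onset on or after the first dose of study drug up to last dose + 30 days". SAP 3.1 keeps off-drug subjects in the endpoint: "Subjects who discontinue study drug but continue to attend study visits (as is the expectation) will have their data assessed for response".

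SAP 6.11.2.3 defines eGFR success for the component tables. One way to succeed is an eGFR below 60 with a confirmed decrease of more than 20% "but with no disease-related or treatment-related eGFR associated AE present at time of assessment". Here the word is AE, not TEAE, and the term list is not repeated. The same section says that the programmed endpoint uses the definition given to the Clinical Endpoints Committee (CEC).

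Protocol 10.3.1 says that, where possible, "the Investigator should report a diagnosis rather than signs and symptoms"; the sentence goes on to include abnormal laboratory values. Once a diagnosis is established, "all previously reported AEs based on signs and symptoms should be nullified and replaced by one AE report".

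**The concern.** This point accepts the sponsor's decision that an eGFR loss should count only when a related renal event comes with it. The difficulty is that the rule can miss such events.

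The TEAE window follows drug exposure, whereas the endpoint follows the subject to Week 52. For a subject who stops early, the two periods separate. A renal event in between can be on the list, be judged disease-related and accompany a confirmed eGFR loss, and the loss is still set aside. Such a subject can be a responder in the primary analysis.

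Separately, a loss recorded only under a renal diagnosis that is not among the seven terms may also be set aside.

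**Working it through.** **1. The plan's own figure, for scale.** Inputs from SAP 4: 20.0% v 34.4%, two-sided 0.05, 80% power, continuity-corrected chi-square, 162 per arm.
- Uncorrected: n' = [1.960·√(2·0.272·0.728) + 0.842·√(0.2·0.8 + 0.344·0.656)]² / 0.144² ≈ 148.7, i.e. 149.
- Corrected: n = (n'/4)·[1 + √(1 + 4/(n'·0.144))]² ≈ 162.3, i.e. 163 when rounded up, against 162 stated. Power at 162 is 79.9%. The plan's figure reproduces.
- One subject changing status moves an arm's response rate by 1/162 = 0.6 points.

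**2. The window.** Take Week w as day 7w. TEAE onset closes at day 7w + 30 for a last dose at Week w. The uncovered time to Week 52 is 364 − (7w + 30).

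| Last dose | Window closes | Days uncovered to day 364 |
|---|---|---|
| Week 12 | 84 + 30 = 114 | 250 |
| Week 20 | 140 + 30 = 170 | 194 |
| Week 24 | 168 + 30 = 198 | 166 |
| Week 36 | 252 + 30 = 282 | 82 |

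The Week 52 date itself lies outside the window for any last dose before day 364 − 30 = 334 (Week 47.7).

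**3. A constructed subject.** Last dose is at Week 20. Baseline eGFR is 80, and Weeks 42, 48 and 52 give 50, 48 and 47, with UPCR 0.4, no rescue and no excess steroid. RENAL IMPAIRMENT, judged disease-related, starts at Week 42.
- The falls are 30/80 = 37.5%, 32/80 = 40% and 33/80 = 41%, all to below 60 and on consecutive visits more than 3 days apart. The loss is confirmed.
- Onset is at day 42 × 7 = 294, which is 294 − 170 = 124 days after the window closed. The event is on the list and related, but it is not a TEAE.

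**4. The same subject under each section.**

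| Section | Wording | Result |
|---|---|---|
| SAP 3.1 and 6.11.1 | TEAE | eGFR loss not used; criterion met; responder |
| SAP 6.11.2.3, component tables | AE | related AE present; not an eGFR success |
| SAP 6.11.2.3, programmed endpoint | same definition as the CEC | follows 6.11.1; responder |

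So a programmed responder would be tabulated as failing the combined UPCR-and-eGFR component. The two wordings cannot both stand.

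**5. The term list.** Protocol 7.6.1.1 names lupus renal flare as a possible contributor to an eGFR decrease. It is not among the seven terms. A related loss reported only as a flare has no listed term under 6.11.1. Under 6.11.2.3, which speaks only of an AE that affects eGFR, it may have a qualifying one.

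**6. Would another analysis show it?** The sensitivity analyses in SAP 6.11.2.2 change only the logistic model. The programmed endpoint keeps the condition. The tipping point analysis in 6.11.2.4 concerns missing data. None re-analyses response with the window or list changed. Adjudicated Week 24 response, a key secondary endpoint, uses similar definitions (6.11.3.4) and would inherit the same wording.

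**The case against.** The strongest case against runs as follows.

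- **Reporting.** A reader might infer that sites must report diagnoses, so that laboratory terms vanish from the database. The documents do not say so. Protocol 10.3.1 says where possible and should. Its replacement sentence names signs and symptoms, not laboratory values. Protocol 10.2.5 allows a laboratory change to be an AE, and Protocol 1.2.5 shows that decreased GFR was recorded as a TEAE in Phase 2. Three of the seven terms are conditions, so a diagnosis is not automatically off the list. This stands, and it makes the list the smaller gap.
- **Adjudication.** The CEC receives eGFR and AE data, its charter is not available here, and the SAP's lead-in says only that a disqualifying value should be accompanied by a TEAE. But the next sentence in 6.11.1 is binding, and the autonomy given to the CEC is stated for rescue medication. The programmed endpoint has no discretion on eGFR.
- **Ongoing events.** The SAP does not say whether a TEAE that began inside the window and is still present at the assessment satisfies the rule. It may. The window gap is therefore limited to new onset after the window, and it would be wrong to infer that the eGFR criterion can never fail off drug.
- **Disclosure.** SAP 6.11.2.3 tabulates confirmed losses without a related AE, and 6.11.4.2 reports confirmed falls of more than 30% with no AE condition. This helps in part. As worded, though, the first table would not count the subject in step 3, who does have a related AE, and neither table re-analyses response.

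**Conclusion.** The point holds as a defect in the definition. Under SAP 3.1 and 6.11.1 as written, a confirmed, related eGFR loss with new onset more than 30 days after last dose cannot count against response, and 6.11.2.3 treats the same subject the other way. The list gap is real but depends on how sites report and how terms are coded.

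The size is not known. It depends on how many subjects stop drug early, stay to Week 52, have a late related renal event and otherwise meet the response criteria. The documents give none of these.

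Two stronger readings should be resisted. A reader might take the Phase 2 discontinuations for decreased GFR (6.7% low dose v 1.1% placebo, Protocol 1.2.5) as the number misclassified. Those are TEAEs of a listed kind, which the rule already catches, so they do not estimate what it misses. A reader might also infer that the gap favours voclosporin. Events that begin over 30 days after last dose may well be disease-driven and can occur in either arm. No direction is shown, so no inflation of the odds ratio or loss of power is claimed.

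**What to change.** 1. In SAP 3.1 and 6.11.1, replace TEAE in the eGFR condition by any treatment- or disease-related AE with onset from first dose up to the Week 52 assessment. Use the same wording and the same term list in 6.11.2.3, so that adjudicated response, programmed response and the component tables agree. State whether an event already ongoing at the first low eGFR qualifies. Carry the wording to Week 24 response, with onset up to that assessment.
2. Before database lock and blinded to arm, review the coded renal terms and settle an extended list that includes renal diagnoses.
3. Confirm that AEs are recorded for off-drug subjects through Week 52. The Schedule of Events asks for them at every visit, but Protocol 10.3.1 can end AE reporting at Visit 16, which Protocol 9.2.4 places 4 weeks after last dose.

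The TEAE definition for the safety tables need not change. The cost is a small change of wording and programming, one blinded term review, and possibly a few more non-responders.

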## 6.11.2 Primary Efficacy Analysis

### 6.11.2.1 Renal response at Week 52

Renal response at Week 52 will be adjudicated by the Clinical Endpoints Committee (CEC) and as such the analysis will incorporate the CEC's assessments of each subject. In order to perform their adjudication, the CEC will be provided UPCR data, eGFR data, steroid taper data, rescue and prohibited medication data and adverse event data. Full details of the adjudication process are detailed in a separate CEC Charter.

The primary efficacy analysis will be conducted on the ITT population using a logistic regression model with terms for treatment, baseline UPCR, biopsy class, MMF use at baseline and region, and renal response (Yes/No) at week 52 as the response variable (Table 14.2.1.1.2).

The results will be expressed as an odds ratio (and associated two sided- 95% CI) for voclosporin compared to placebo. Odds ratios greater than unity will mean the odds of response are greater for voclosporin than for placebo and therefore indicate a benefit of the voclosporin treatment arm. The p-value of the treatment effect will also be reported.

The following SAS program will be used for the primary efficacy analysis:

```
Proc Logistic data = data;  
Class Treatment_arm MMF_Use Biopsy_Class Region;  
Model Response = Treatment_arm MMF_Use Biopsy_Class Baseline_UPCR Region;  
Run;
```

The number of responders and non-responders at Week 52 will be summarized by treatment arm and a listing of renal responders and non-responders will also be provided.

#### **6.11.2.2 Sensitivity Analyses of the Primary Endpoint**

The primary endpoint of adjudicated renal response at Week 52 in the ITT population will be analyzed using two different logistic regression models. The first sensitivity analysis will include only a term for treatment while the second sensitivity analysis will include terms for treatment, baseline UPCR, biopsy class and MMF use at baseline (i.e., omitting the regional covariate). Results will be reported in Table 14.2.1.2. The Odds ratios, 95% confidence intervals and p-values for voclosporin compared to placebo will be reported.

- The primary endpoint will also be analyzed, using the same ITT population, controlling in turn for each the following factors:
  - age ( $\leq 30$  versus  $>30$ ),
  - gender,
  - race (White, Asian, Other),
  - biopsy class,
  - region (defined at the continental level and, where numbers allow, country level),
  - MMF use at screening,
  - Maximum MMF Dose ( $\leq 2g$  versus  $>2g$ ).

- An interaction between the factor and treatment group will be added to the model. A p-value for the main effect of the covariate in question along with the p-value for the interaction between treatment and covariate will be reported (Tables 14.2.1.7.1-7).

These sensitivity analyses will be performed on the same endpoint in the same population as set out in the primary analysis section; the only difference being the logistic models.

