### 7.2.2.3 Mycophenolate Mofetil (Background Therapy)

Subjects receiving MMF prior to randomization will continue without interruption.

- Subjects must be counselled on the risk of pregnancy while taking MMF and the need for adequate contraceptive precautions (see Section 5.4, [Adequate/Effective Contraception](#)).
- Subjects on AZA or mycophenolate sodium at screening must switch to MMF at baseline (Day 1).
- For subjects who are not already taking prescribed MMF prior to randomization, the dosing of MMF will start at 500 mg BID for a total daily dose of 1 g/day for the first week, increasing to 1 g BID for a total daily dose of 2 g/day for the second and subsequent weeks (i.e., beginning on Day 8).
- Complete blood count must be performed locally at Weeks 1 and 3 in subjects not already taking MMF at screening (unscheduled visit or not).

All subjects will take MMF BID (morning and evening), before meals (i.e., on an empty stomach), with a glass of water. If a dose is missed, the subject should take the next correct dose rather than “doubling up” at the next dosing time point. A stable dose of MMF will be maintained throughout the study. Dose changes or interruptions are permitted for clearly documented safety reasons only.

- Approval by the Medical Monitor is required for subjects taking a dose other than 2 g/day MMF from randomization onwards (e.g., total daily dose of 1 or 3 g/day).
- If GI disturbance or other side-effects occur with MMF, the 1 g BID dosing may be changed to 500 mg four times daily.
- If a subject has an ANC  $<1,500/\text{mm}^3$  at any study visit, the dose of MMF should be decreased or interrupted. If a subject has an ANC  $<1,000/\text{mm}^3$  at any visit, the dose should be discontinued and only recommenced when the ANC reaches  $1,500/\text{mm}^3$ . If the subject has a dose interruption of MMF of  $>14$  days, then permanent discontinuation of MMF, therefore the study, should be considered after discussion with the Medical Monitor.
- If deemed necessary by the Investigator on account of leukopenia or other adverse effect, or if the subject weighs 50 kg or less, the dose of MMF may be decreased to a minimum of 500 mg BID.

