**AMENDMENTS BEFORE DATABASE LOCK**

Version	Issue Date	Section	Revision/Addition	Rationale
2.0	Jul 2018	6.11.2.2 11	Adding additional covariate to the sensitivity analysis for the primary endpoint. Covariate will be MMF $\leq 2$ g versus MMF $> 2$ g. MMF dose to be defined as each patient's maximum dose during the study.	To assess possible differences between responses for patients taking higher levels of MMF.
2.0	Jul 2018	6.11.2.3 11	Component analysis for primary endpoint to be undertaken for both Adjudicated response and programmed response	To ensure full details of the analysis are available should differences between adjudicated response and programmed response become apparent.
2.0	Jul 2018	6.11.2.2 11	Sensitivity analysis using regional covariate will be defined at both continental and country level	To ensure sufficient information is available re: regional differences.
2.0	Jul 2018	6.11.3.3	Confirming Week 24 Renal Response will be a programmed endpoint only. This will not be adjudicated by the CEC	Ensuring consistency between the SAP and the CRC charter
2.0	Sep 2018	6.13.1	Updating assumptions for missing AE relationships	Ensure definitions are as per current requirements
2.0	Sep 2018	5 6.2.12 9	Confirming that region (used as blocking factor) will be in the primary model	Regulatory Agency feedback requesting clarification
2.0	Sep 2018	6.11.1	Adding clarification around the make-up of the CEC: blind and independent	Regulatory agency feedback
2.0	Sep 2018	6.11.1	Adding rescue medication clarifications	Regulatory Agency feedback
2.0	Sep 2018	6.11.2.1 6.11.2.2 6.11.2.3	Adding clarification around the sensitivity analyses, supplementary analyses and the tipping point analysis.	Regulatory agency feedback

2.0	Sep 2018	3.1	Clarifying that subjects who withdraw from the study are defined as non-responders	Regulatory Agency feedback
2.0	Sep 2018	3.2.1 3.2.2 9	Duration of UPCR $\leq 0.5$ moved from key secondary to other secondary	Regulatory Agency feedback
2.0	Sep 2018	1	Clarification around IV methylprednisolone	Ensure consistency with protocol
2.0	Sep 2018	6.4	Clarification withdrawal versus discontinuation	Ensure consistent use throughout the SAP
2.0	Sep 2018	6.11.3.2 6.11.3.3 6.11.4.1 6.11.4.2 6.11.4.3 6.11.4.4	Referencing baseline section for endpoints that use non-standard calculations	Ensure baseline calculations are clear for each endpoint

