## 6.11 Efficacy Analyses

All statistical tests will be performed using a two-tailed 5% overall significance level, unless otherwise stated. All comparisons between treatments will be reported with 95% confidence intervals for the odds ratio, hazard ratio or difference as applicable.

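### One sensitivity model of the primary endpoint conditions on maximum on-study MMF dose, a post-randomisation variable, so its covariate and interaction p-values can be distorted in either direction

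*SAP*

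**What the plan says.** SAP 6.11.2.2 (Sensitivity Analyses of the Primary Endpoint) first describes two alternative logistic models: treatment only, and the primary model without region. For these it states: "The Odds ratios, 95% confidence intervals and p-values for voclosporin compared to placebo will be reported".

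It then lists seven factors to be controlled for one at a time: age, gender, race, biopsy class, region, MMF use at screening, and "Maximum MMF Dose" split at 2 g. For each, "An interaction between the factor and treatment group will be added to the model". The outputs named are the p-value for the covariate's main effect and a "p-value for the interaction between treatment and covariate will be reported". The section closes: "These sensitivity analyses will be performed on the same endpoint in the same population as set out in the primary analysis section", adding that only the logistic models differ.

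Section 6.11.2.2 does not define the dose variable. The definition is in the SAP table of amendments before database lock (version 2.0), which gives each patient's "maximum dose during the study". That entry introduced a covariate that still stands in the current text, so it is the only definition available. The stated reason is to look for differences in response among patients on higher MMF doses.

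On whether MMF dose can move after randomisation:

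- Protocol 7.2.2.3: "Dose changes or interruptions are permitted for clearly documented safety reasons only". Doses other than 2 g/day need Medical Monitor approval, and 3 g/day is one of the examples given.
- SAP 6.11.1: any MMF dose is permitted, and no dose level necessarily counts as rescue.
- Protocol 5.6.1: once study treatment is permanently discontinued, further treatment is left to the Investigator. Under SAP 3.1 such subjects are still assessed for response if they keep attending visits.

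**The concern.** Six of the seven factors cannot be affected by the assigned treatment. Maximum on-study dose can be. If a subject who is not improving has MMF raised above 2 g, and voclosporin changes how many subjects improve early, then the subjects above 2 g are selected differently in the two arms. A comparison within dose strata is then no longer the randomised comparison behind the primary estimand, so this model differs from the primary analysis in more than its covariates.

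Two readings of the output could go wrong. An interaction p-value could be taken as evidence that the benefit of voclosporin depends on MMF dose when it reflects selection into the >2 g group. A covariate p-value could be taken as an effect of MMF dose on response when it reflects poor response leading to a higher dose. The sensitivity label invites a conclusion about robustness that the model cannot support.

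**Working it through.** **1. The plan's own figure.** Inputs from SAP section 4: 20.0% v 34.4%, two-sided 0.05, 80% power, continuity-corrected chi-square, 162 per arm. The mean rate is 0.272 and the difference 0.144.

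- Uncorrected: n = {1.960√(2×0.272×0.728) + 0.842√(0.200×0.800 + 0.344×0.656)}² / 0.144² = 148.7.
- Corrected: (n/4){1 + √(1 + 4/(n×0.144))}² = 162.3, or 163 rounded up. Power at 162 is 79.9%, so the plan's figure reproduces.
- Design odds ratio: (0.344/0.656)/(0.200/0.800) = 2.098.

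**2. Set-up.** These are exact population calculations, not simulations. The overall response rates stay at 20.0% and 34.4%, and MMF dose has no effect on response. The documents give neither the share above 2 g nor its relation to arm, so these are assumptions: 5% above 2 g at entry, plus a fraction e of early non-responders escalated. With the effect wholly through early response, 20% (placebo) and 40% (voclosporin) respond early, and final response is 0.776 after early response and 0.056 otherwise. Check: 0.2×0.776 + 0.8×0.056 = 0.200, and 0.4×0.776 + 0.6×0.056 = 0.344.

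**3. One case in full (e = 20%).** P(>2 g) is 0.05 in early responders and 0.05 + 0.95×0.20 = 0.24 in the rest.

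- Placebo above 2 g: share 0.2×0.05 + 0.8×0.24 = 0.202. Response (0.2×0.05×0.776 + 0.8×0.24×0.056)/0.202 = 0.0916.
- Voclosporin above 2 g: share 0.4×0.05 + 0.6×0.24 = 0.164. Response (0.4×0.05×0.776 + 0.6×0.24×0.056)/0.164 = 0.1438.
- Odds ratio above 2 g: (0.1438/0.8562)/(0.0916/0.9084) = 1.67, against a true 2.10.

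**4. Range.** The main-effects model contains treatment and dose group only.

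| Assumption about who exceeds 2 g | Main-effects OR | OR ≤2 g | OR >2 g |
|---|---|---|---|
| Fixed before randomisation, 10% per arm | 2.10 | 2.10 | 2.10 |
| e = 5 / 10 / 20 / 40 / 60%, effect wholly through early response | 2.09 / 2.09 / 2.06 / 2.00 / 1.89 | 2.05 to 2.11 | 1.97 / 1.85 / 1.67 / 1.46 / 1.35 |
| e = 5% to 40%, effect partly through early response* | 2.02 to 2.10 | 1.82 to 2.07 | 2.41 to 3.01 |
| e = 20% placebo, 10% voclosporin | 1.96 | 1.93 | 2.33 |
| e = 10% placebo, 20% voclosporin | 2.20 | 2.30 | 1.32 |
| e = 30% placebo, 10% voclosporin | 1.82 | 1.75 | 2.64 |
| Depends only on final response | 2.10 | 2.10 | 2.10 |

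*Early response 30% v 50%. Final response after early response is 0.35 or 0.45 in both arms; otherwise it is set to keep 20.0% and 34.4%.

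**5. The named interaction p-value.** The largest expected signal relative to its standard error is the partial case with e = 40%. The ratio of stratum odds ratios is 3.006/1.818 = 1.65, log 0.503. Cell sizes (162 × share) are 51.2 and 38.9 above 2 g, and 110.8 and 123.1 at or below. Response rates in the same order are 0.146, 0.339, 0.225 and 0.3455. The sum of 1/{np(1−p)} is 0.359, so SE = 0.60 and z = 0.503/0.60 = 0.84. A nominal 5% test then rejects with probability Φ(−1.12) + Φ(−2.80) ≈ 13%. In the opposite direction the ratio is 1.317/2.303 = 0.57, and the same steps give SE 0.93, z = −0.60 and about 9%.

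**6. The named covariate p-value.** Suppose dose depends only on final response, with P(>2 g) 0.05 in responders and 0.24 in non-responders. The treatment odds ratio does not move, because both arms' odds within a stratum are multiplied by the same factor. The covariate odds ratio is (0.05/0.95)/(0.24/0.76) = 0.17, although dose has no effect on response.

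**The case against.** The strongest case on the other side has four parts.

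**The protocol limits the mechanism.** MMF changes are for documented safety reasons, a stable dose is intended, and doses other than 2 g/day need approval. The provisions for poor response are a pause or step back in the steroid taper (Protocol 7.2.2.2) and stopping study treatment (5.6.1), not more MMF. A safety reduction does not lower a maximum already reached. If this is followed, being above 2 g may largely reflect dose at entry, and there is then no distortion. This stands as a limit on likelihood. It does not close the route, given SAP 6.11.1 and the discretion left after discontinuation.

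**A reader might infer that the SAP will publish a biased treatment odds ratio.** The section does not say so. For the factor models it names only the covariate and interaction p-values, and a model with an interaction has no single treatment odds ratio. The odds-ratio sentence belongs to two models without this factor. An odds ratio follows only from the general rule in SAP 6.11: "All comparisons between treatments will be reported with 95% confidence intervals for the odds ratio, hazard ratio or difference as applicable". A reader might also infer that bias is certain, or always towards no effect. The documents give no escalation rates, and the calculation goes both ways.

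**The shifts are small against sampling error.** At 162 per arm the SE of the log odds ratio is √{1/(162×0.2×0.8) + 1/(162×0.344×0.656)} = 0.257. Moving from 2.098 to 1.82 is 0.142 on the log scale, or 0.55 SE; moving to 2.20 is 0.19 SE. This stands for the main-effects odds ratio. The stratum contrast moves more.

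**The question is exploratory, and a pre-randomisation dose does not answer it.** This also stands. It is a reason to label the on-study model exploratory, not to keep it among the sensitivity analyses. A pre-randomisation grouping overlaps with MMF use at screening but remains well defined, since subjects not on MMF fall in ≤2 g.

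**Conclusion.** The point holds as a matter of what the model conditions on and how it is labelled. Maximum on-study MMF dose is post-randomisation, and the documents leave room for it to respond to treatment. Its covariate and interaction p-values, and any odds ratio shown with them, can therefore be distorted, in a direction that cannot be known in advance.

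Under the assumed mechanisms the main-effects odds ratio lies between 1.82 and 2.20 against 2.10, and the odds ratio above 2 g between about 1.3 and 3.0. A nominal 5% interaction test rejects up to about 13% of the time with no effect of MMF dose. These figures rest wholly on assumed escalation rates. The treatment comparison does not move if dose is fixed before randomisation or depends only on final response, though in the latter case the covariate p-value still misleads.

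It would be wrong to read this as a threat to the primary result. The primary model uses MMF use at baseline, and the primary test, the Hochberg family and the type I error are untouched. The change is worth making but is not critical.

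**What to change.** In SAP 6.11.2.2, replace the seventh factor with MMF dose recorded before randomisation, ≤2 g (including subjects not taking MMF) versus >2 g, and define it there.

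For maximum on-study dose, do one of two things:

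- tabulate it by arm descriptively; or
- move the model out of the sensitivity analyses, label it exploratory and not causal, and state the definition in that section rather than only in the amendment table.

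Reconcile Protocol 7.2.2.3 with SAP 6.11.1 on permitted MMF dosing. This review takes no view on which is right.

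The cost is a few lines of SAP text and a revised table. No new data are needed: Protocol 7.5.3 already requires MMF dose records, and concomitant medications are recorded from screening. The downside is that the amendment's question about higher on-study doses would be answered only descriptively or in an exploratory analysis. If few subjects are above 2 g before randomisation, the replacement model will also be imprecise.
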